#### 7.3 CAUSALITY

A complete assessment of the causality must always be made by a medically qualified doctor who is registered on the delegation of responsibility log; this is usually the investigator.

If any doubt about the causality exists, the local investigator should inform SCTU who will notify the Chief Investigator. Other clinicians may be asked for advice in these cases.

In the case of discrepant views on causality, SCTU will classify the event as per the worst case classification and if onward reporting is required, the MHRA and/or REC will be informed of both parties' points of view.

Relationship	Description	Denoted
Not related	Relationship to the device or procedures can be excluded when:	SAE
	The event is not a known side effect of the product category the device belongs to, or of similar devices and procedures	
	
 
The event has no temporal relationship with the use of the investigational device or the procedures
 
	
	
 
The event does not follow a known response pattern to the medical device, and is biologically implausible
 
	
	
 
The discontinuation of medical device application (or the reduction of the level of activation/exposure [when clinically feasible]) and reintroduction of its use (or increase the level of activation/exposure), do not impact on the serious event
 
	
	The event involves a body-site or an organ not expected to be affected by the device or procedure	
	
 
The serious event can be attributed to another cause (e.g. an underlying or concurrent illness/clinical condition, an effect of another device, drug, treatment or other risk factors)
 
	

Unlikely	
 
The event does not depend on a false result given by the investigational device used for diagnosis, when applicable
 
Harms to the subject are not clearly due to use error In order to establish the non-relatedness, not all the criteria listed above might be met at the same time, depending on the type of device/procedures and the serious event.
 
The relationship with the use of the device seems not relevant and/or the event can be reasonably explained by another cause, but additional information may be obtained
 
	SAE
Possible	The relationship with the use of the investigational device is weak but cannot be ruled out completely. Alternative causes are also possible (e.g. an underlying or concurrent illness/clinical condition or/and an effect of another device, drug or treatment).  Cases where relatedness cannot be assessed or no information has been obtained should also be classified as possible.	Anticipated or Unanticipated Serious Adverse Device Effect (ASADE or USADE)
Probable	The relationship with the use of the investigational device seems relevant and/or the event cannot reasonably be explained by another cause, but additional information may be obtained.	Anticipated or Unanticipated Serious Adverse Device Effect (ASADE or USADE)
Causal relationship	The serious event is associated with the investigational device or with procedures beyond reasonable doubt when:  The event is a known side effect of the product category the device belongs to or of similar devices and procedures  The event has a temporal relationship with investigational device use/application or procedures  The event involves a body-site or organ that  The investigational device or procedures are applied to;  The investigational device of procedures have an effect on  The serious event follows a known response pattern to the medical device (if the response pattern is previously known)  The discontinuation of medical device application (or reduction of the level of activation/exposure) and reintroduction of its use (or increase of the level of activation/exposure) impacts on the serious event (when clinically feasible)  Other possible causes (e.g. an underlying or concurrent illness/clinical condition or/and an effect of another device, drug or treatment) have been adequately ruled out  Harm to the subject is due to error in use  The event depends on a false result given by the investigational device used for diagnosis (when applicable)  In order to establish the non-relatedness, not all the criteria listed above might be met at the same time, depending on the type of device/procedures and the serious event.	Anticipated or Unanticipated Serious Adverse Device Effect (ASADE or USADE)

## 7.4 EXPECTEDNESS

Expectedness assessments are made against the list of expected events as detailed in the IB and referred to in sections 7.4.1 and 7.4.2 below. The nature and/or severity of the event should be considered when making the assessment of expectedness. If these factors are not consistent with the current information available, then the AE or device deficiency should be recorded as 'unexpected'.

## 7.4.1 Device Deficiencies

- Insertion (difficulty to advance because of stent buckling on the side hole)
- Removal (stent fracturing on side holes)
- Encrustation and biofilm formation (E&B) leading to failure to drain
- Functional challenges (failing to drain)

## 7.4.2 Adverse Events

- Cystitis (and associated symptoms)
- Urinary tract infection (and associated symptoms)
- Haematuria
- Loin pain
- Encrustation and biofilm formation

#### 7.5 REPORTING PROCEDURES

Any questions concerning adverse event reporting should be directed to the SCTU in the first instance. A flowchart will be provided to aid in the reporting procedures.

# 7.5.1 Reporting Details

# 7.5.1.1 Adverse Events

All AEs that are related to the experimental stent, or that relate to the medical condition requiring the stent should be recorded on the eCRF as per the trial specific requirements listed in Section 7.2.1.

# 7.5.1.2 Device Deficiencies

All device deficiencies should be sent to the CASSETTE SCTU Trial Team via email (**only those not relating to a participant**) or recorded on the Device Deficiency eCRF as per the trial specific requirements listed in section 7.2.2.

#### 7.5.1.3 Serious Adverse Events

For all reportable SAEs and device deficiencies, an SAE report form should be completed with as much detail as possible (including any relevant anonymised treatment forms and/or investigation reports) and emailed to SCTU immediately but at least within 3 days of site becoming aware of the event.

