## SAE REPORTING CONTACT DETAILS

Please email a copy of the SAE form to SCTU within 3 days of becoming aware of the event

Email: [contact]

FAO: Quality and Regulatory Team

For further assistance: [contact] (Mon to Fri 09:00 – 17:00)

The event term should be the most appropriate medical term or concept (for adverse events) or technical term or concept (for device deficiencies) in the opinion of the assessing investigator.

Additional information should be provided as soon as possible if all information was not included at the time of reporting.

As per regulatory and local SCTU procedures, all SAEs and device deficiencies that might have led to an SAE as detailed in section 7.2.2 will be reported to the MHRA. Additionally, SAEs will be reported to the REC, if the event was:

- 'Related' i.e., resulted from the administration of any of the research procedures; and
- 'Unexpected' i.e., an event that is not listed in the CIP as an expected occurrence.

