## 7.6 RESPONSIBILITIES

# 7.6.1 Principal Investigator (PI)

The PI, or medically qualified doctor who is registered on the delegation of responsibility log, is responsible for:

- 1. Using medical judgement in assigning seriousness, causality and if requested, whether the event was anticipated using the expectedness information approved for the trial (as detailed in Section 7.4)
- 2. Ensuring that all reportable SAEs and device deficiencies are recorded and reported to the SCTU immediately, or at least within 24 hours, of becoming aware of the event and provide further follow-up information as soon as available. Ensuring that reportable events are chased with the SCTU if a record of receipt is not received within 1 working day of initial reporting.
- 3. Ensuring that AEs are recorded and reported to the SCTU in line with the requirements of the CIP.
- 4. Delegated Chief Investigator responsibilities detailed in section 7.6.2 below.

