## 9.2 DEVIATIONS AND SERIOUS BREACHES

## 9.2.1 Clinical Investigation Plan Compliance

A CIP deviation is any noncompliance with the CIP or Good Clinical Practice (GCP) requirements. Any deviation occurring at sites should be reported to the SCTU and the local R&D Office immediately. As a result of deviations SCTU will advise of and/or undertake any corrective and preventative actions as appropriate. Deviations from the CIP which are found to frequently recur are not acceptable, will require immediate action and could potentially be classified as a serious breach.

Manufacturers (or SCTU if delegated in the Task Allocation Matrix) must notify the MHRA of all deviations relating to UK study sites as soon as they have been made aware of them. Details about the nature of the deviation, when it occurred, where it occurred, and any proposed corrective and preventative actions should be provided. MHRA provides details on how to report if this, if this is delegated to SCTU, then local processes will be followed.

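### The outer limit for sites to report SAEs and reportable device deficiencies to SCTU is 3 days in section 7.5.1.3 and the SAE contact box, but 24 hours in section 7.6.1

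*Protocol*

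**What the plan says.** Three places in the protocol set a limit for the site's report to SCTU.

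- **Section 7.5.1.3 (Serious Adverse Events).** Scope: "For all reportable SAEs and device deficiencies, an SAE report form should be completed with as much detail as possible". The form is to be emailed to SCTU "immediately but at least within 3 days of site becoming aware of the event".
- **SAE reporting contact details box.** "Please email a copy of the SAE form to SCTU within 3 days of becoming aware of the event".
- **Section 7.6.1 item 2 (Principal Investigator).** The PI, or a delegated doctor, is responsible for "Ensuring that all reportable SAEs and device deficiencies are recorded and reported to the SCTU", and the time allowed is "immediately, or at least within 24 hours, of becoming aware of the event".

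Section 9.2.1 defines what follows from missing a limit: "A CIP deviation is any noncompliance with the CIP or Good Clinical Practice (GCP) requirements". It requires sites to report deviations to SCTU and the local R&D office at once. It requires the MHRA to be told of all deviations at UK sites, and it warns that frequent recurrence could be classed as a serious breach.

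**The concern.** The reporting procedure and the contact box are what site staff will have open when an event occurs, and both give 3 days. The PI's list of duties, against which a monitor may check the site, gives 24 hours. Nothing in the protocol says which prevails, and the summary of changes in section 19 does not mention the difference.

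Two things are at stake. First, for a report made on the second or third day, the document cannot settle whether a deviation has occurred, yet section 9.2.1 attaches regulatory notification to that answer. Second, section 7.6.4 gives the sponsor or its delegate expedited reporting duties to the MHRA and REC within required timelines, and the site's report is the first link in that chain.

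**Working it through.** No sample size, power or event count is involved, so the check compares the texts.

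| Element | Section 7.5.1.3 and contact box | Section 7.6.1 item 2 |
|---|---|---|
| Events | reportable SAEs and device deficiencies (the box refers to the SAE form) | reportable SAEs and device deficiencies |
| Sender | site | site PI or delegated doctor |
| Recipient | SCTU | SCTU |
| Clock starts | awareness of the event | awareness of the event |
| Immediate reporting asked for | yes in 7.5.1.3; not repeated in the box | yes |
| Outer limit | 3 days | 24 hours |

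**Size of the gap.** Reading 3 days as 3 × 24 = 72 hours (an assumption, since the protocol does not define the day count), the gap is 72 − 24 = 48 hours.

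**Compliance by time of report, judged on the outer limits:**
- up to 24 hours: inside the limit in all three places;
- more than 24 and up to 72 hours: inside the limit in 7.5.1.3 and the box, outside it in 7.6.1, and so a deviation under 9.2.1;
- more than 72 hours: outside the limit in all three.

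The conflict therefore runs one way. A site can meet the 3-day limit and miss the 24-hour one, but not the reverse.

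**Can the texts be reconciled as they stand?**
- *Notification within 24 hours, form within 3 days.* Section 7.2.3 requires serious events to be reported to SCTU on the SAE report form, and section 7.2.2 uses the same form for qualifying device deficiencies. Reporting to SCTU in 7.6.1 therefore means that form. The telephone route in 7.5.1.3 is for advice and is followed by the emailed form.
- *Initial report against follow-up.* Both 7.6.1 and the text below the contact box deal with later information separately, without a fixed limit. The 24 hours and the 3 days both apply to the first report.
- *The 3 days in section 7.7.* That is a duty of the CI and sponsor to tell the MHRA and REC about urgent safety measures. It does not explain a site deadline.

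**Effect on onward reporting.** The protocol does not state the sponsor's timelines or when they start. If they start at site awareness, a report at the 3-day limit uses up to 48 hours more of them than one at the 24-hour limit. If they start at receipt by SCTU, it uses none. The range is 0 to 48 hours.

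**The case against.** The best defence is that sections 7.5.1.3 and 7.6.1 both ask for immediate reporting. A report held until day 3 without reason would not clearly satisfy even the longer text, so the gap is not 48 hours on every event. A site can also comply with the whole document by reporting within 24 hours. Both points stand, and they limit the finding to the outer limits. They do not remove it, because an outer limit is what a monitor can check, and the protocol has two.

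A second defence is that 7.5.1.3 concerns a detailed form with supporting reports, while 7.6.1 speaks of initial reporting and allows follow-up later. That hints at a two-step scheme, but the protocol states none, and sections 7.2.2 and 7.2.3 point the other way.

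A reader might infer something stronger: that in a first-in-human trial which keeps recruiting during its safety reviews, the reporting lag decides how many more stents go in before the stopping counts are updated. The documents do not support this. Tables 1 and 2 in section 3.1 count insertion problems, fractures at removal and removals within 7 days of insertion. They do not count SAE forms, and the insertion item is labelled as not severe. Events and device deficiencies at surgery go onto the trial database, and the rules are applied at set reviews. Even if the link were granted, the planned 50 patients over 12 months at a uniform rate (an assumption) give 50/365 × 2 = 0.27 insertions in 48 hours across both cohorts, or about 0.55 at twice that rate.

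**Conclusion.** The contradiction is in the current text and should be corrected. For the same reports, the outer limit is 72 hours in two places and 24 hours in a third. A report made between those limits meets the first two and is a deviation, notifiable to the MHRA, under the third. It may also take up to 48 hours from the sponsor's onward reporting time, depending on when that clock starts.

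The conclusion rests on reading 3 days as 72 hours and on the SAE report form being the reporting route in both sections. It does not extend to the stopping rules, and it does not touch the primary endpoint, sample size, analysis populations or estimates. The documents do not show which deadline was intended.

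**What to change.** State one outer limit and use it in section 7.5.1.3, the SAE contact box and section 7.6.1 item 2. Before fixing it, check it against the sponsor's onward reporting timelines under section 7.6.4. If a two-step scheme is wanted, with an early notification and a fuller form later, the protocol should say so and give each step its own limit. Until the texts agree, a report within 24 hours satisfies all three.

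The cost is a short amendment in three places and a notice to the two sites. Under section 9.3 the amendment must be notified to the MHRA and REC and takes effect only once authorised. No change to data collection or analysis is needed.

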#### Or

Contact SCTU by phone for advice and then email a scanned copy of the SAE report form completed as above.

## SAE REPORTING CONTACT DETAILS

Please email a copy of the SAE form to SCTU within 3 days of becoming aware of the event

Email: [contact]

FAO: Quality and Regulatory Team

For further assistance: [contact] (Mon to Fri 09:00 – 17:00)

The event term should be the most appropriate medical term or concept (for adverse events) or technical term or concept (for device deficiencies) in the opinion of the assessing investigator.

Additional information should be provided as soon as possible if all information was not included at the time of reporting.

As per regulatory and local SCTU procedures, all SAEs and device deficiencies that might have led to an SAE as detailed in section 7.2.2 will be reported to the MHRA. Additionally, SAEs will be reported to the REC, if the event was:

- 'Related' i.e., resulted from the administration of any of the research procedures; and
- 'Unexpected' i.e., an event that is not listed in the CIP as an expected occurrence.

## 7.5.1.4 Reporting Timelines

All CIP reportable AEs and SAEs should be reported from date of day of insertion of novel ureteric stent up until the date of the return of the last questionnaire, the date of the follow up phone call, or the date of the qualitative interview for patients that consent to the qualitative sub-study, whichever is the later.

All unresolved adverse events should be followed up by the investigator until one of the end of trial criteria is met (i.e. lost to follow up, withdrawal etc.). Upon receiving the last completed post-surgery questionnaire from the participant, or upon completion of the qualitative interview, the investigator should instruct each participant to report any subsequent event(s) that the participant believes might reasonably be related to participation in this trial. The investigator should notify the trial sponsor of any death or adverse event occurring at any time after a participant has discontinued or terminated trial participation that may reasonably be related to this trial.

## 7.5.2 Pre-existing Conditions

- Pre-existing conditions (prior to informed consent) should not be reported as an AE unless the conditions worsen during the trial. Instead, they will need to be recorded on the Medical History eCRF, within the trial database.

## 7.5.3 Pregnancy

Pregnancy is not considered an AE unless a negative or consequential outcome is recorded for the mother or child/foetus. If the outcome meets the serious criteria, this would be considered an SAE and should be reported as detailed in section 7.5.1.

- 1) Pregnancy prior to stent insertion is an exclusion criterion and must result inpatient withdrawal. These pregnancies do not need to be followed up, but 'pregnancy' should be captured on the EoS form.
- 2) Participants who become pregnant after stent removal (Surgery 2) will not need to be withdrawn, nor will their pregnancies need to be followed up. The dates of the pregnancy will be required to be recorded to ensure that follow-up is not needed. This will need to be documented on the pregnancy notification form.
- 3) Pregnancies that occur in participants whilst a novel stent is in situ will require a pregnancy notification form to be completed on the eCRF. These pregnancies should be followed up by site until at least birth (if consent from participant is obtained for this).

## 7.6 RESPONSIBILITIES

# 7.6.1 Principal Investigator (PI)

The PI, or medically qualified doctor who is registered on the delegation of responsibility log, is responsible for:

- 1. Using medical judgement in assigning seriousness, causality and if requested, whether the event was anticipated using the expectedness information approved for the trial (as detailed in Section 7.4)
- 2. Ensuring that all reportable SAEs and device deficiencies are recorded and reported to the SCTU immediately, or at least within 24 hours, of becoming aware of the event and provide further follow-up information as soon as available. Ensuring that reportable events are chased with the SCTU if a record of receipt is not received within 1 working day of initial reporting.
- 3. Ensuring that AEs are recorded and reported to the SCTU in line with the requirements of the CIP.
- 4. Delegated Chief Investigator responsibilities detailed in section 7.6.2 below.

## 7.6.2 Chief Investigator (CI) / delegate or independent clinical reviewer:

The Chief Investigator (CI) is responsible for delegating the following responsibilities to each Principal Investigator at their relevant site for:

- 1. Clinical oversight of the safety of patients participating in the trial, including an ongoing review of the risk/benefit.
- 2. Upon request review coding decisions

## 7.6.3 Independent clinical reviewer

The delegated clinical reviewer is responsible for the below tasks. The Principal Investigator for each site will have the responsibility of clinically reviewing and providing a second opinion on all SAE's that occur at each other's site.

- 1. Using medical judgement in assigning the SAEs seriousness, causality and whether, if requested, the event was anticipated (in line with the expectedness information) where it is required as a second clinical opinion or if it has not been possible to obtain local medical assessment.
- 2. Immediate review of all USADEs
- 3. Review of specific SAEs and related SAEs in accordance with the trial risk assessment and CIP as detailed in the Trial Monitoring Plan.

# 7.6.4 Sponsor / delegate

The Sponsor, or delegate, is responsible for:

- 1. Central data collection and verification of device deficiencies, AEs and SAEs, according to the CIP onto a database/paper forms.
- 2. Reporting safety information to the independent clinical reviewer(s) for the ongoing assessment of the risk / benefit according to the Trial Monitoring Plan.
- 3. Checking causally related events against the approved expectedness information, in place at time of event onset.
- 4. Reporting safety information to the Data Monitoring & Ethics Committee (DMEC) according to the Trial Monitoring Plan.
- 5. Ensuring the expedited reporting of all reportable SAEs and device deficiencies to the Competent Authority (MHRA in UK) within required timelines
- 6. Ensuring expedited reporting of related and unexpected serious adverse events to the REC within the required timelines.
- 7. Notifying Investigators of related and unexpected serious adverse events that occur within the trial.
- 8. Quarterly reporting of summary SAE data to the Competent Authority (MHRA in UK)
- 9. Notifying PIs of updates to the Reference Safety Information for the trial.

## 7.7 REPORTING URGENT SAFETY MEASURES

If any urgent safety measures are taken the CI/Sponsor shall immediately, and in any event no later than 3 days from the date the measures are taken, give written notice to the MHRA and REC of the measures taken and the circumstances giving rise to those measures.

# 8 STATISTICS AND DATA ANALYSES

## 8.1 ANALYSIS POPULATIONS

Intention-to-treat (ITT) population: All patients entered in the trial. Safety population: All patients who attempted to insert the stent. As-treated population: All patients who completed Surgery 1.

Per-protocol population: All patients who completed Surgeries 1 and 2

#### 8.2 METHOD OF RANDOMISATION

Not applicable.

